#### *7.1.4.2.1.2 Definition of HCV Virologic Failure: Non-response, Rebound, Virologic Breakthrough, and Relapse*

Lack of efficacy at different timepoints in the trial will be categorized as:

- Non-response: Subject has HCV RNA detected at end of treatment without HCV RNA <LLOQ on treatment (note that breakthrough is captured elsewhere).
- Rebound: Subject has a rebound defined as  $>1 \log_{10}$  IU/mL increase in HCV RNA from nadir while on treatment and confirmed from a separate blood draw within 2 weeks.
- Virologic breakthrough: Subject has a confirmed HCV RNA  $\geq$ LLOQ [TD quantifiable (TD[q])] after being <LLOQ previously while on treatment. Confirmation is defined as an HCV RNA  $\geq$ LLOQ from a separate blood draw repeated within 2 weeks.
- Relapse: Subject has a confirmed HCV RNA  $\geq$ LLOQ [TD(q)] following end of all study therapy, after becoming undetectable (TND) at end of treatment. Confirmation is defined as an HCV RNA  $\geq$ LLOQ from a separate blood draw repeated within 2 weeks.

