### 7.1.4.2 Assessment of Viral Load

#### 7.1.4.2.1 Measurement of HCV RNA

HCV-RNA levels in plasma will be measured using the Roche COBAS® AmpliPrep/COBAS TaqMan HCV Test, v2.0 on blood samples drawn from each subject at various time points prior to, during, and after dosing, as indicated in the Study Flow Chart (Section 6.0). Samples are collected and processed as per instructions provided.

Results from the sample collected at the screening visit are used to determine eligibility. Samples collected at other time points are used for efficacy analyses. They are also used to identify subjects who meet HCV virologic failure criteria. The nomenclature detailed in Table 12 will be used when describing HCV RNA levels.

Table 12 Nomenclature for Describing HCV RNA Levels

Abbreviation	Definition	HCV RNA level
TND	Target not detected	HCV RNA not detected
TD(u)	Target detected but unquantifiable	HCV RNA <LLOQ
TD(q)	Target detected, quantifiable	HCV RNA ≥LLOQ

Abbreviations: HCV = hepatitis C virus; LLOQ = lower limit of quantification.

The LLOQ of the COBAS test is 25 IU/mL and its limit of detection is 15·IU/mL. We define virological breakthrough to be confirmed HCV RNA concentration of at least 25 IU/mL after a previous value of less than 25 IU/mL. We define relapse as a confirmed HCV RNA concentration of at least 25 IU/mL following an undetectable (HCV RNA <15·IU/mL) the at end of treatment. For both virological breakthroughs and relapses, we defined confirmation as an HCV RNA concentration of at least 25 IU/mL from a separate blood draw repeated within 2 weeks.

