#### *7.1.4.2.1.1 Definition of Efficacy Endpoints*

Efficacy will be defined at different timepoints during the trial. Specific endpoints are:

- SVR4: The subject has HCV RNA <LLOQ [either TD(u) or TND] 4 weeks after the end of all study therapy.
- SVR12: The subject has HCV RNA <LLOQ [either TD(u) or TND] 12 weeks after the end of all study therapy.
- SVR24: The subject has HCV RNA < LLOQ [either TD (u) or TND] 24 weeks after the end of all study therapy.

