#### **7.1.4.2.2 Viral Resistance Measurements and Mechanisms**

##### HCV resistance measurements

# Proprietary Information of MD Anderson

Protocol # 2016-0251

Date: February 24, 2020

98

Resistance-associated variants of the HCV can lead to failure of therapy. This is one of the most important considerations when treating with some DAAs. To better understand the potential for RAVs with either grazoprevir and/or elbasvir, samples will be retained at virologic failure confirmation visits, and RAVs will be assessed for any subject who has detectable virus above 1000 IU/mL and has met an HCV virologic failure criteria. To limit the risk of RAVs, subjects are not allowed to have monotherapy with grazoprevir or elbasvir in this protocol.

Blood samples for viral resistance assays are collected at screening and Day 1 Cycle 1 to determine resistance to grazoprevir and/or elbasvir. Additional resistance testing on these samples may be performed. Blood samples for resistance testing are also collected during the follow-up period, as well as at the virologic failure confirmation visit for genotypic and investigational assays to assess resistance to grazoprevir and elbasvir.

In a pooled analysis of subjects treated with regimens containing Zepatier with or without RBV in Phase 2 and 3 clinical trials, resistance analyses of both drug targets were conducted for 50 subjects who experienced virologic failure and had sequence data available (6 with on-treatment virologic failure, 44 with post-treatment relapse). Treatment-emergent substitutions observed in the viral populations of these subjects based on HCV GTs and subtypes are shown in Table 13. Treatment-emergent NS5A substitutions were detected in 30/37 (81%) GT1a-, 7/8 (88%) GT1b-, and 5/5 (100%) GT4-infected subjects. The most common treatment-emergent NS5A substitutions in GT1a were at position Q30 (n=22). Treatment-emergent NS3 substitutions were detected in 29/37 (78%) GT1a-, 2/8 (25%) GT1b-, and 2/5 (40%) GT4-infected subjects. The most common treatment-emergent NS3 substitutions in GT1a were at position D168 (n=18). Treatment-emergent substitutions were detected in both HCV drug targets in 23/37 (62%) GT 1a-, 1/8 (13%) GT1b-, and 2/5 (40%) GT4-infected subjects.

Table 13. Treatment-Emergent Amino Acid Substitutions Among Virologic Failures in the Pooled Analysis of ZEPATIER with and without Ribavirin Regimens in Phase 2 and Phase 3 Clinical Trials

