# Proprietary Information of MD Anderson

Protocol # 2016-0251

Date: February 24, 2020

119

The HCV RNA outcome is categorized as TND, TD(u), and TD(q). There are 3 types of missing data handled by different approaches.

1. Intermittent missing: If a missing data point is immediately preceded and followed by non-missing HCV RNA outcomes, the missing value would be imputed to the worse outcome of the two. For example, if a missing data point is preceded by TD(q) and followed by TD(u) or TND, then the missing value would be imputed as TD(q); if a missing data point is preceded by TD(u) and followed by TND, then the missing value would be imputed as TD(u); when a missing value is flanked by two TND, then the missing value would be imputed as TND.
2. Non-intermittent missing related to the study drug: For missing values due to premature study discontinuations due to treatment related reasons either for safety or efficacy, the missing values will be considered as treatment failures.
3. Non-intermittent missing unrelated to the study drug: For missing data due to premature study discontinuations with reasons unrelated to treatment such as loss to follow-up, protocol violation, withdrawal of consent, administrative reasons, etc., the missingness mechanism is unlikely to be related to subjects' response to the HCV treatment, and therefore the missing at random (MAR) assumption is reasonable. The approaches to address this type of missing data depend on the analytical strategy, and they are described in the following sections.

In addition, a missing baseline/Day1 HCV RNA result will be replaced with a screening result, if available.

Approaches to handle non-intermittent missing values due to prematurely discontinuing from the study:

- Treatment-Related Discontinuation = Failure (TRD=F) approach: The treatment related type 2 missing will be considered as failure; whereas the subjects who have the type 3 missing value and do not have virologic failure during the observed study period will be excluded from the analysis for the time points following their study withdrawal. Note that subjects with documented virologic failure during the treatment or follow-up period, even if they withdrew prematurely due to reasons not related to study drug, are classified as failures.
- Missing = Failure (M=F) approach: Any non-intermittent missing (i.e., the type 2 and 3 missing) will be imputed as failure, regardless of the reason for study discontinuation.

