## 8.13.5 Subject Virologic Failure: Non-response, Rebound, Breakthrough, and Relapse

Summary statistics will be provided to describe the rates of occurrence of subject virologic non-response, rebound, breakthrough, and relapse. Definitions for subject virologic onresponse, rebound, breakthrough, and relapse are in Section 4.2.4.3.1.2. Viral resistance testing will focus on the entire NS3/4A and NS5A regions for all subjects and for those who meet the subject virologic failure criteria.

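### Relapse requires an undetectable end-of-treatment result while SVR accepts TD(u), so a subject who ends HCV therapy at TD(u) and then rises is either uncategorised or labelled a breakthrough

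*Combined protocol and SAP*

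**What the plan says.** Section 7.1.4.2.1 gives the assay limits: "The LLOQ of the COBAS test is 25 IU/mL", with a limit of detection of 15 IU/mL. Table 12 separates three states: TND (not detected), TD(u) (detected, below the LLOQ) and TD(q) (at or above the LLOQ).

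Success is set at the LLOQ. For SVR12, Section 7.1.4.2.1.1 says: "The subject has HCV RNA <LLOQ [either TD(u) or TND] 12 weeks after the end of all study therapy".

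Relapse is set lower, and is worded in two places. Section 7.1.4.2.1 requires a confirmed value of at least 25 IU/mL "following an undetectable (HCV RNA <15·IU/mL) the at end of treatment". Section 7.1.4.2.1.2 requires a confirmed TD(q) result "following end of all study therapy, after becoming undetectable (TND) at end of treatment".

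Breakthrough also has two wordings. Section 7.1.4.2.1 says: "We define virological breakthrough to be confirmed HCV RNA concentration of at least 25 IU/mL after a previous value of less than 25 IU/mL". It sets no limit on when the rise occurs. Section 7.1.4.2.1.2 mentions being on treatment, but does not make clear whether that qualifies the earlier low value or the later rise.

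Three parts of the plan use these categories. Section 8.13.5: "Summary statistics will be provided to describe the rates of occurrence of subject virologic non-response, rebound, breakthrough, and relapse". Section 7.1.4.2.2: "RAVs will be assessed for any subject who has detectable virus above 1000 IU/mL and has met an HCV virologic failure criteria". Section 8.13.3, under TRD=F, says that subjects who leave for unrelated reasons and "do not have virologic failure during the observed study period will be excluded from the analysis" for the time points after they withdraw.

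**The concern.** A set of failure categories should give each failure exactly one label. Here the success threshold and the relapse threshold do not meet. A subject at TD(u) at end of treatment satisfies the SVR threshold at that visit, yet cannot be a relapse whatever happens afterwards.

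TD(u) at end of treatment is an outcome the plan expects. The exploratory HCV endpoints in Section 8.13.1 report TND and TD(u) at Week 12 or Week 16, which are the ends of the 12- and 16-week regimens.

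What is at stake is mainly whether the relapse and breakthrough rates in Section 8.13.5 mean what their names say. Two analysts following different sections could report different rates from the same data. Section 8.13.5 does not settle the matter, because it refers for its definitions to Section 4.2.4.3.1.2, and no definition is found there.

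**Working it through.** The plan states no figure that rests on these definitions, so there is none to reproduce. The check sets the definitions side by side for two Arm B subjects. Both have a confirmed HCV RNA at or above the LLOQ after HCV therapy has ended. One was TD(u) at end of treatment, the other TND. The end-of-treatment sample is taken as on treatment.

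| Definition | TD(u) at end, then rise | TND at end, then rise |
|---|---|---|
| Non-response (7.1.4.2.1.2) | No: was <LLOQ on treatment | No |
| Rebound (7.1.4.2.1.2), rise must be on treatment | No | No |
| Breakthrough (7.1.4.2.1.2), rise must be on treatment | No | No |
| Breakthrough (7.1.4.2.1.2), only the earlier <LLOQ value on treatment | Yes | Yes |
| Breakthrough (7.1.4.2.1) | Yes | Yes |
| Relapse (either section) | No: not undetectable | Yes |

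There are two alternative results.

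- **Narrow reading** (Section 7.1.4.2.1.2, rise on treatment only): the TD(u) subject has no category and the TND subject is a relapse. The categories have a gap.
- **Broad reading** (Section 7.1.4.2.1, or Section 7.1.4.2.1.2 with only the earlier value on treatment): the TD(u) subject is a breakthrough, and the TND subject is both a breakthrough and a relapse. The categories overlap.

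There are two edge cases. If the end-of-treatment sample is not counted as on treatment and no earlier value was <LLOQ, the TD(u) subject becomes a non-response. Rebound has the same ambiguity as breakthrough: if being on treatment qualifies only the nadir, a post-treatment rise of more than 1 log10 could be called a rebound.

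**After the change.** With relapse set at <LLOQ (TD(u) or TND) at end of treatment and breakthrough limited to on-therapy rises, both subjects are a relapse and nothing else. Changing the relapse threshold alone would leave the overlap with breakthrough.

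**Illustration of the TRD=F effect.** The counts are assumed; 15 is the planned arm size. Suppose one subject is TD(u) at end of treatment, has a confirmed rise, withdraws for an unrelated reason before the week-12 sample, and is held to have no virologic failure. TRD=F then removes that subject from the denominator. Intervals are exact 95% Clopper-Pearson.

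- 13 successes: 13/15 = 86.7% (59.5 to 98.3) becomes 13/14 = 92.9% (66.1 to 99.8), a shift of 6.2 points.
- 14 successes: 14/15 = 93.3% (68.1 to 99.8) becomes 14/14 = 100% (76.8 to 100), a shift of 6.7 points.

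Under Missing = Failure the subject is a failure either way, so there is no shift.

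**Context.** In the pooled Zepatier data in Section 7.1.4.2.2, 44 of 50 virologic failures with sequence data were post-treatment relapses (44/50 = 88%). Relapse is thus the main failure mode in that series. The figure does not say how many of the 44 were TD(u) at end of treatment.

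**The case against.** The strongest reply is that this is a labelling problem and that the more serious consequences a reader might infer do not follow. Most of that stands.

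- **Bias in the primary SVR12 rate.** A reader might infer that the Arm B primary result is inflated. The documents do not support that as a general statement. SVR12 in anyone with a week-12 sample depends only on that value. Section 8.13.3 does not name TRD=F as primary and also gives Missing = Failure. It further keeps as failures those with documented virologic failure in treatment or follow-up, without tying this to the four labels; a confirmed rise in follow-up could reasonably be read as covered. An unconfirmed rise would not be a relapse even from TND, so the effect needs a confirmed one.
- **Lost resistance data.** The trigger in Section 7.1.4.2.2 does require a failure criterion. However, Section 4.3.4.2 tests any subject above 1000 IU/mL after Zepatier with no category needed, and both the HCV Markers text in Section 4.3.4.6 and Section 8.13.5 refer to all subjects. Resistance testing is mostly covered.
- **Gap and overlap together.** They arise under different readings and should not be added. On the broad reading the TD(u) subject is a documented failure and stays in the denominator.
- **Inability to separate on-treatment from post-treatment failure.** Sample dates against the last HCV dose would still separate them. The defect is in the labels, and the data to repair it exist.

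The reply does not remove the mismatch. Both relapse wordings require an undetectable result, SVR does not, and no other section assigns the TD(u) subject. The broad reading of breakthrough fills the gap only by giving a post-treatment event an on-treatment name and by labelling TND relapsers twice.

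**Conclusion.** The point holds as a defect in the definitions. A subject who is TD(u) at the end of HCV therapy and then has confirmed HCV RNA at or above the LLOQ is either in no failure category or is a breakthrough, depending on which section and reading is used. On the second reading, TND relapsers carry two labels.

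The main consequence is for the descriptive rates in Section 8.13.5, where post-treatment relapse can be omitted, mislabelled or counted twice. How often this would happen is unknown. It depends on the share of subjects at TD(u) at end of treatment, which the documents do not give. In an arm of about 15, each affected subject is about 7% of the arm (1/15 = 6.7%).

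The effect on SVR12 is secondary. It needs all of the following: TD(u) at end of treatment, a confirmed rise, an unrelated withdrawal before the week-12 sample, the narrow reading of breakthrough, a reading of Section 8.13.3 that ties failure to the four labels, and use of TRD=F. The shift of about 6 to 7 points is an illustration on assumed counts, with heavily overlapping intervals. The importance is modest, and the correction is worth making because it is specific and nearly free.

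**What to change.** In both Section 7.1.4.2.1 and Section 7.1.4.2.1.2:

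- Define relapse as confirmed HCV RNA at or above the LLOQ after the end of HCV therapy, in a subject whose end-of-treatment HCV RNA was <LLOQ (TD(u) or TND). This replaces the undetectable, <15 IU/mL and TND conditions.
- Limit breakthrough to rises in samples taken on HCV therapy. Word rebound the same way.
- State that the end-of-treatment sample counts as on treatment, so that non-response and relapse cannot both apply.

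Then use this single set for the Section 8.13.5 summaries, the Section 7.1.4.2.2 resistance trigger and the TRD=F rule in Section 8.13.3, and correct the cross-reference in Section 8.13.5.

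The cost is a few sentences, made by amendment before database lock. No new samples or assays are needed, because the planned test already distinguishes TND, TD(u) and TD(q). The downside is that the reported relapse rate may rise slightly.

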#### **7.1.4.2.2 Viral Resistance Measurements and Mechanisms**

##### HCV resistance measurements

# Proprietary Information of MD Anderson

Protocol # 2016-0251

Date: February 24, 2020

98

Resistance-associated variants of the HCV can lead to failure of therapy. This is one of the most important considerations when treating with some DAAs. To better understand the potential for RAVs with either grazoprevir and/or elbasvir, samples will be retained at virologic failure confirmation visits, and RAVs will be assessed for any subject who has detectable virus above 1000 IU/mL and has met an HCV virologic failure criteria. To limit the risk of RAVs, subjects are not allowed to have monotherapy with grazoprevir or elbasvir in this protocol.

Blood samples for viral resistance assays are collected at screening and Day 1 Cycle 1 to determine resistance to grazoprevir and/or elbasvir. Additional resistance testing on these samples may be performed. Blood samples for resistance testing are also collected during the follow-up period, as well as at the virologic failure confirmation visit for genotypic and investigational assays to assess resistance to grazoprevir and elbasvir.

In a pooled analysis of subjects treated with regimens containing Zepatier with or without RBV in Phase 2 and 3 clinical trials, resistance analyses of both drug targets were conducted for 50 subjects who experienced virologic failure and had sequence data available (6 with on-treatment virologic failure, 44 with post-treatment relapse). Treatment-emergent substitutions observed in the viral populations of these subjects based on HCV GTs and subtypes are shown in Table 13. Treatment-emergent NS5A substitutions were detected in 30/37 (81%) GT1a-, 7/8 (88%) GT1b-, and 5/5 (100%) GT4-infected subjects. The most common treatment-emergent NS5A substitutions in GT1a were at position Q30 (n=22). Treatment-emergent NS3 substitutions were detected in 29/37 (78%) GT1a-, 2/8 (25%) GT1b-, and 2/5 (40%) GT4-infected subjects. The most common treatment-emergent NS3 substitutions in GT1a were at position D168 (n=18). Treatment-emergent substitutions were detected in both HCV drug targets in 23/37 (62%) GT 1a-, 1/8 (13%) GT1b-, and 2/5 (40%) GT4-infected subjects.

Table 13. Treatment-Emergent Amino Acid Substitutions Among Virologic Failures in the Pooled Analysis of ZEPATIER with and without Ribavirin Regimens in Phase 2 and Phase 3 Clinical Trials

Target	Genotype 1a N = 37	Genotype 1b N = 8	Genotype 4 N = 5
NS5A	M28A/G/T, Q30H/K/R/Y, L31F/M/V, H58D, Y93H/N/S	L28M, L31F/V, Y93H	L28S/T, M31I/V, P58D, Y93H
NS3	V36L/M, Y56H, V107I, R155I/K, A156G/T/V, V158A, D168A/G/N/V/Y	Y56F, V107I, A156T	A156M/T/V, D168A/G, V170I

## Persistence of Resistance-Associated Variations

The persistence of elbasvir and grazoprevir treatment-emergent amino acid substitutions in NS5A and NS3, respectively, was assessed in HCV GT1-infected subjects in Phase 2 and 3

# Proprietary Information of MD Anderson

Protocol # 2016-0251

Date: February 24, 2020

99

trials whose virus had treatment-emergent RAVs in the drug target, and with available data through at least 24 weeks post-treatment using population nucleotide sequence analysis.

Viral populations with treatment-emergent NS5A RAVs were generally more persistent than those with NS3 RAVs. Among GT1a-infected subjects, NS5A RAVs persisted at detectable levels at follow-up week 12 in 95% (35/37) of subjects and in 100% (9/9) of subjects with follow-up week 24 data. Among GT1b-infected subjects, NS5A RAVs persisted at detectable levels in 100% (7/7) of subjects at follow-up week 12 and in 100% (3/3) of subjects with follow-up week 24 data.

Among GT1a-infected subjects, NS3 RAVs persisted at detectable levels at follow-up week 24 in 31% (4/13) of subjects. Among GT1b-infected subjects, NS3 RAVs persisted at detectable levels at follow-up week 24 in 50% (1/2) of subjects.

Due to the limited number of GT4-infected subjects with treatment-emergent NS5A and NS3 RAVs, trends in persistence of treatment-emergent substitutions in this GT could not be established.

The lack of detection of a virus containing a RAV does not necessarily indicate that viral populations carrying that substitution have declined to a background level that may have existed prior to treatment. The long-term clinical impact of the emergence or persistence of virus containing Zepatier-RAVs is unknown.

## Effect of Baseline HCV Amino Acid Polymorphisms on Treatment Response in Genotype 1-Infected Subjects

Analyses using population nucleotide sequencing were conducted to explore the association between NS5A or NS3 amino acid polymorphisms and treatment response among treatment-naïve and treatment-experienced GT1-infected subjects. Baseline NS5A polymorphisms at resistance-associated positions (focusing on any change from subtype reference at NS5A amino acid positions 28, 30, 31, or 93) were evaluated. Baseline NS3 polymorphisms at positions 36, 54, 55, 56, 80, 107, 122, 132, 155, 156, 158, 168, 170, or 175 were evaluated. Analyses of SVR12 rates pooled data from subjects naïve to DAAs and who received Zepatier with or without RBV in Phase 3 clinical trials, and censored subjects who did not achieve SVR12 for reasons unrelated to virologic failure.

### *Genotype 1a*

In GT1a-infected subjects, the presence of 1 or more HCV NS5A amino acid polymorphisms at position M28, Q30, L31, or Y93 was associated with reduced efficacy of Zepatier for 12 weeks (Table 14), regardless of prior treatment history or cirrhosis status. The prevalence of polymorphisms at any of these positions in GT1a-infected subjects was 11% (62/561) overall, and 12% (37/309) specifically for subjects in the US. across Phase 2 and Phase 3 clinical trials evaluating Zepatier for 12 weeks or Zepatier plus RBV for 16 weeks. The prevalence of polymorphisms at these positions in GT1a-infected subjects was

